Missing data intermittently during the study and/or dropouts are inevitable and an issue faced by all longitudinal studies, although recent evidence indicates relatively low levels of attrition for randomized trials in a military context (Adler, Williams, et al., 2015). There is no consensus, however, on the optimal analytical strategy to analyze missing data. Using the standard missing data taxonomy (Rubin, 1987), we will follow the recommendations made by Nich and Carroll (1997, 2002) and conduct intent-to-treat analyses using three strategies. In the first strategy we will extend the multiple imputation method of Little and Yau (1996) to allow for non-monotone missing values, which could occur intermittently during the study period. Monotone missing patterns require subsequent variables to be missing once a variable is missing. We will impute unobserved outcomes based on study condition, observed subject-level covariates at baseline and observed follow-ups. Inferences will be made on imputed datasets using Rubin's method (Barnes, Lindborg, & Seaman, 2006; Rubin, 1996). Our second analytical strategy will consider selection models and pattern-mixture models (Michiels, Molenberghs, Bijnens, Vangeneugden, & Thijs, 2002) based on different factorization of the joint distribution of the response variables and the missing patterns. As different strategies require different assumptions for the estimated treatment effects to be unbiased and some assumptions are not testable, comparisons of these strategies serve mainly as sensitivity analyses of their influence on the estimated key parameters of each Aim. A third strategy will consider the use of Full Information Maximum Likelihood methods in the analysis of incomplete data as implemented in several software programs (e.g., Mplus; Muthén & Muthén, 2007). As mentioned in the prior section, this study is adequately powered for an attrition rate of 20%.

9. Privacy, Confidentiality, and Data Security

Confidentiality:

- All devices that can link to OHSU or house OHSU data are required to have Symantec Whole Desk Encryption software installed. All data will be stored on secure, password protected servers.
- Methods of sharing data will NOT include the use of email or thumb drives, but rather by IRB approved methods, such as Box.com, which is sanctioned by OHSU's IRB.
- Any contact information, including mailing address, email and phone numbers for participants will be kept separate from any files containing survey data. We will only have this contact information from platoon leaders and unit POCs (not soldiers). Only a few key staff members will have access to these files with contact information, generally those who need to interact with participants for incentive payments or for reminders to complete a survey or training.
- If there is a reasonable expectation of harm to self or others, staff are expected to break confidentiality by reporting this to the proper authorities. This information is included in the Informed Consent.
- We have included a statement in the Informed Consent stating that representatives of USAMRMC (DoD) may review our study records to ensure we are compliant with our research protocols.

Disposition of Data:

- Electronic data will be stored primarily on the secure OHSU servers, which is encrypted and password protected.
- Any hard copies of data will be kept in a locked file cabinet in the project office, which is also locked when no one is present.
- De-identified data will be kept indefinitely on the secure servers at OHSU.
- Any contact information for participants will be destroyed at the end of the project.
- The project manager will be primarily responsible for ensuring data are secure and protocols are followed by all approved and trained staff.
 - We will have a data sharing agreement that details these protocols to ensure the confidentiality and integrity of the data. A signed copy stating they will comply with these protocols must be on file with the project manager before an individual is granted access to data, as well as a valid reason for having access (e.g., a paper proposal).
 - All individuals who will have contact with data and/or participants will have a copy of a record of Human Subjects training on file.

10. Provisions to Monitor the Data to Ensure the Safety of Subjects

We will prepare this if the study is deemed to be more than Minimal Risk.

11. Risks and Benefits

a. Risks to Subjects

Foreseeable risks:

Efforts will be made to minimize risks associated with this study. Minimal potential risks for participation include breaches of confidentiality associated with data collected for research purposes. In addition, there is a risk of psychological distress associated with the psychological distress survey measures. Additional potential, but not expected, risk is that a supervisor may be

upset about being contacted to participate in a study or may not like the training. Leaders can discuss these issues at any time with research staff.

Risk management and emergency response:

To mitigate potential distress related to the psychological well-being survey items, participants will be made aware that participation is completely voluntary and that they are welcome to not answer any questions participants find distressing or to withdraw involvement at any moment without consequence. On the information sheet, we will provide contact information for behavioral health resources at OHSU.

Confidentiality:

Several processes are put in place to mitigate against breach of confidentiality for survey and training data:

- All devices that can link to OHSU or house OHSU data are required to have Symantec Whole Desk Encryption software installed. All data will be stored on secure, password protected servers.
- Methods of sharing data will NOT include the use of email or thumb drives, but rather by IRB approved methods, such as OneDrive, which is sanctioned by OHSU's IRB.
- If we collect any contact information, including mailing address, email and phone numbers for participants will be kept separate from any files containing survey data. We will only have this contact information from department heads. Only a few key staff members will have access to these files with contact information.
- If there is a reasonable expectation of child abuse, staff are expected to break confidentiality by reporting this to the proper authorities. This information is included in the Informed Consent.
- In the event we have any hard copies of data, they will be kept in a locked file cabinet in the project office, which is also locked when no one is present.
- De-identified data will be kept indefinitely on the secure servers at OHSU.
- Any contact information for participants will be destroyed at the end of the project.
- The project manager will be primarily responsible for ensuring data are secure and protocols are followed by all approved and trained staff.
 - We will have a data sharing agreement that details these protocols to ensure the confidentiality and integrity of the data. A signed copy stating they will comply with these protocols must be on file with the project manager before an individual is granted access to data, as well as a valid reason for having access (e.g., a paper proposal).
 - All individuals who will have contact with data and/or participants will have a copy of a record of Human Subjects training on file.

The Study PI will also follow the University's guidelines for reporting any unanticipated events in a timely fashion and consult with compliance specialists at the university on appropriate responses or additional reporting as needed.

b. Potential Benefits to Subjects

For employees, there is no immediate, direct benefit. We expect that when we train leaders in mental health support, we also may enhance employees' psychological health and attenuate

traumatic situations that could lead to negative behavioral health outcomes. We anticipate that the training program serves as a primary prevention intervention that will have a positive impact on individual health behaviors, including psychological health, risky behaviors, and hazardous alcohol consumption. This training intervention will eventually have the opportunity of being extended and implemented more broadly. The study holds great promise for informing the implementation of evidence-based leadership training programs across workplace settings.

12. Multi-Site Coordination (delete if not applicable)

~~Portland State University is a co-investigation site on our grant; [name], PI for OHSU, also has a dual appointment at PSU and [name] is PI for PSU. All research activities will be overseen by OHSU staff, including recruitment, data collection, and training delivery. The PSU IRB is ceding oversight to OHSU's IRB. Any PSU research assistants will go through the same training as OHSU RAs. The PSU team will be working primarily in providing consultation and writing papers.~~

References Cited

Adler, A. B., Bliese, P. D., Pickering, M. A., Hammermeister, J., Williams, J., Harada, C., ... Ohlson, C. (2015). *Mental skills training with basic combat training soldiers: A group-randomized trial. Journal of Applied Psychology, 100*(6), 1752–1764. <http://dx.doi.org.proxy.lib.pdx.edu/10.1037/apl0000021>

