Specific Aim 3: To test the effects of the RESULT training compared to the control group on perceptions of increased leadership resilience-supportive behaviors from the perspective of the service members, following the training (Hypothesis 2).

Specific Aim 4: To test the effects of the RESULT training compared to the control group on behavioral health measures such as emotion regulation, connectedness, team cohesion, psychological health, and physical health following the training (Hypotheses 3 & 4).

Specific Aim 5: Translate the tenets of the RESULT to other branches of services, and other employee populations who would benefit, such as first responders.

Study Hypotheses

- 1) Leaders in the intervention group will report positive reactions to the training and will demonstrate increased knowledge from pre-test to post-test.
- 2) Service Members in the intervention group will report improved perceptions of resilience-supportive leadership behaviors compared to those in the control group.
- 3) Service Members in the intervention group will report higher levels of resilience-related factors such as adaptive emotion regulation strategies, resilience, social connectedness and belongingness, and team cohesion, compared to those in the control group.
- 4) Service Members in the intervention group will report higher levels of resilience-related outcomes such as psychological and physical health and well-being, compared to those in the control group.

3. Background

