All study staff dealing with both participants and/or data will have completed sanctioned Human Subject Research training. The PI and Project Manager both have experience with DoD-regulated research and reviewed these regulations with the DoD Science Officer after the grant was awarded. They will both be responsible for training any new study staff with regard to these specific DoD regulations.

b. Survey Measures

We will collect sociodemographic data and military experience, including military work history, combat exposure and deployment history. Our survey outcome measures will map on to our hypotheses to ensure we can evaluate between- and within-group effects. We will also ask which specific unit to which they are currently assigned so we can nest data within units and account for unit-level similarities (see Statistical Analysis below). Some of the hypotheses include data that are not from the surveys, such as training data (pre- and post-tests) (see Hypothesis 1), but we will track that information as well and merge with survey data. Table 1 includes a summary of proposed measures, sources, and when and from whom they will be collected. All proposed measures have been used in previous research and are psychometrically sound. A list of individual surveys items are included in our submission.

Hypothesis 2 will be evaluated with a measure assessing the leader's support for resilience within their unit. This measure, commensurate with previous work we have done (e.g., Family-Supportive Supervisor Behaviors and Sleep Leadership), will be developed based on tenets of the intervention. It will be measured from the perspective of the subordinates (e.g., "My platoon leadership team supports resilience in our unit"). Before reporting any

findings on Hypothesis 2, we will examine the psychometric properties of the adapted measure to ensure reliability and validity.

The bulk of the survey will be comprised of measures that assess Hypotheses 3 and 4. Hypothesis 3 is specific to perceptions around resilience factors such as social connectedness, resilience, and emotional regulation, whereas Hypothesis 4 is specific to perceptions around resilience-related outcomes including psychological, physical health, and well-being.

Table 1. Summary of Survey Measures

Concept	Measure	Reference	# of Items	When collected*	Who*	Hyp.
Leader Training Data	Leader reactions to training	Adapted from [name] et al. (2011)	3	T	PLT	1

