	Knowledge of resilience leadership	Adapted from [name] et al. (2011)	3	T	PLT	1
Resilience-supportive Behaviors	RSLB measure adapted from VSSB and FSSB (Service Member's Ratings of Leaders)	Adapted from Perry et al. (2018) and [name] et al. (2009, 2013)	3-5	S	SM	2
	Perceived Leader Effectiveness	Adapted from Ragins 1989 by WRAIR	5	S	SM	2
	General Supervisor Support	Yoon & Lim (1999)	3	S	SM	2
Emotion Regulation	Reappraisal and Emotion Suppression	Gross & John (2003)	10	S	SM	3
Resilience	Brief Resilience Scale	Smith et al. (2008)	6	S	SM	3
	CD-RISC (Brief Connor-Davidson Resilience)	Campbell-Sills & Stein (2007)	10	S	SM	3
Social Connectedness	Thwarted Belongingness Subscale	Hill et al. (2015).	5	S	SM	3
	Brief Loneliness Scale	Hughes, et al. (2004)	3	S	SM	3

Psychological Health	K6 Psychological Distress	Kessler et al. (2002)	6	S	SM	4
	Functional Impairment (WRAIR)	Herrell et al. (2014)	13	S	SM	4
	Perceived Stress Scale (PSS)	Cohen et al. (1983)	4	S	SM	4
	PTSD (PCL-5)	Price et al. (2016)	4	S	SM	4
	Dimensions of Anger (DAR-5)	Forbes et al. (2014)	5	S	SM	4
Physical Health	Sleep Problems	Jenkins et al. (1988)	4	S	SM	4
	General Perceived Health	Hobfoll et al. (2012)	4	S	SM	4
	Chronic Pain	Mattacola et al. (1997)	1	S	SM	4
	Alcohol misuse (AUDIT-C)	Bush et al. (1998)	3	S	SM	4
Unit Cohesion	Unit Cohesion	Williams et al. (2016)	8	S	SM	4
Demographics	Brief Combat Exposure	WRAIR		T S	PLT, SM	
	Unit info, age, rank, gender, Relationship Status, # of Children,			T S	PLT, SM	
	Years in military, deployment history,					
	Months in platoon					

*NOTE: T = Training; S = Survey; PLT = Platoon Leadership Team; SM = Service Member

c. Sharing of Results with Subjects

We currently do not have plans to share results with participants participating in the survey. Leaders in the treatment group will receive the results of their pre- and post-test on the training. Results of the study will be shared with the leadership at JBLM, but only at an aggregate level.

8. Data Analysis

a. Statistical Plan and Data Analysis

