Hypothesis 3 assesses the effect of the intervention on the soldiers' resilience-related factors such as adaptive emotion regulation strategies, resilience, social connectedness and belongingness. . Estimates of the effect of similar interventions on adaptive emotion regulation vary widely [e.g., $d = .26$ in Bentley, et al. (2018); $d = .30$ in Cameron, Carroll & Hamilton (2018); and $d = .90$ in Mahatmya, Thurston, & Lynch (2018)]. Estimates of the effect of similar interventions on prosocial connections tend to be small in size [e.g., $d = .205$ for organizational citizenship behaviors in [name], et al. (2016)]. Using the smallest of these effect size estimates for the power analysis for H3, we estimate power to be .80 in the current study.

Hypothesis 4 assesses the effect of the intervention on the soldiers' resilience-related outcomes such as psychological and physical health and well-being. Estimates of the effect of similar interventions on health outcomes tend to be small in size [e.g., $d = .26$ for physical health in [name], et al. (2011); $d = -.217$ for blood pressure in [name], et al. (2015)]. Using the smallest of these effect size estimates for the power analysis for H4, we estimate power to be .84 in the current study.

In summary, based on the expected sample sizes, participation and attrition rates, and effect sizes (i.e., from the research literature) we are adequately powered to test the 4 study hypotheses.

c. Missing Data and the Application of Intent-to-Treat

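### Team cohesion is named under Hypothesis 3, but its only measure is coded to Hypothesis 4 in Table 1, and neither hypothesis's stated power covers it

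*Combined protocol and SAP*

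**What the plan says.** Cohesion, or a list in which it would be expected, appears in these places:

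- **Section 2, overarching goals.** Goal 2 names unit cohesion among the effects to be evaluated.
- **Section 2, Specific Aim 4.** The aim covers "behavioral health measures such as emotion regulation, connectedness, team cohesion, psychological health, and physical health following the training (Hypotheses 3 & 4"), so it attaches cohesion to the two hypotheses jointly.
- **Section 2, Study Hypotheses.** Hypothesis 3 ends its list with "social connectedness and belongingness, and team cohesion, compared to those in the control group". Hypothesis 4 concerns "resilience-related outcomes such as psychological and physical health and well-being, compared to those in the control group" and does not name cohesion.
- **Section 7b, text before Table 1.** "Hypothesis 3 is specific to perceptions around resilience factors such as social connectedness, resilience, and emotional regulation", while "Hypothesis 4 is specific to perceptions around resilience-related outcomes including psychological, physical health, and well-being". Cohesion is in neither list.
- **Section 7b, Table 1.** The only cohesion row is "Unit Cohesion": 8 items, survey, service members, Hyp. 4.
- **Section 8b, H3 paragraph.** The hypothesis is restated as "resilience-related factors such as adaptive emotion regulation strategies, resilience, social connectedness and belongingness", without team cohesion.

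Section 8a does not list outcomes by hypothesis. Section 8b describes platoon-level ICCs as usually below .04, excepts platoon-level constructs and gives cohesion as the example, then assumes .04 for the power analyses. It reports power of .96 (H2, d = .27), .80 (H3, d = .205) and .84 (H4, d = .217 in size).

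**The concern.** Table 1 is the only place where individual measures are tied to hypotheses, and for cohesion it disagrees with the hypothesis as written. A reader following section 2 would count a cohesion result toward the resilience-factor hypothesis. A reader following Table 1 would count it toward the psychological and physical health hypothesis. A favourable cohesion result could then be presented as evidence on health, and Hypothesis 3 could be judged without one of its named parts. The plan gives no primary outcome and no rule for when a hypothesis with several outcomes counts as supported, so nothing else fixes the choice in advance.

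There is a linked gap in the power section. Cohesion is the one outcome the plan identifies as likely to have a larger ICC, yet both hypotheses it might belong to are powered only at .04. The closing statement that the study is adequately powered for all four hypotheses therefore has no calculation behind it for cohesion, whichever code is right.

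**Working it through.** **1. Assignment of cohesion, place by place**

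| Place | Hypothesis 3 | Hypothesis 4 |
|---|---|---|
| Section 2, hypotheses | named | not named |
| Section 2, Aim 4 | jointly with H4 | jointly with H3 |
| Section 7b, text | not listed | not listed |
| Section 7b, Table 1 | no cohesion row | Unit Cohesion, code 4 |
| Section 8b, power text | not listed | not listed |

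Only the first and fourth rows make a definite assignment, and they conflict. Team and unit cohesion are different labels, but Table 1 has one cohesion measure. If that measure is not the Hypothesis 3 outcome, Hypothesis 3 names something the survey does not measure.

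Counting Table 1 rows as printed, H3 has 5 measures and H4 has 10. Following the hypothesis text gives 6 and 9. The total is 15 either way.

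**2. Reproducing the stated powers**

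Inputs from the documents: n = 1245 at follow-up (section 5a); ICC = .04 and d = .27, .205, .217 (section 8b). Not stated, so assumed: two-sided alpha .05, the total number of platoons K, and the share p of soldiers in the intervention arm.

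Formulas: m = n/K; design effect DE = 1 + (m − 1) × ICC; effective n = n/DE; SE = √[1/(p × n_eff) + 1/((1 − p) × n_eff)]; power = Φ(d/SE − 1.96).

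- *Layout A*, K = 102, p = 7.5/11: m = 1245/102 = 12.21; DE = 1 + 11.21 × .04 = 1.448; n_eff = 859.7; SE = .0732. Power .958, .799, .842.
- *Layout B*, K = 70, p = 1/2: m = 17.79; DE = 1 + 16.79 × .04 = 1.671; n_eff = 744.9; SE = .0733. Power .958, .799, .842.

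Both round to the stated .96, .80 and .84, so the plan's figures are attainable at an ICC of .04. They do not identify the layout. Section 5a gives about 102 leadership teams as the number targeted for training in 7-8 of the 11 battalions, so 102 as the overall total is an assumption. Reading 102 as the intervention arm of 8 in 11 battalions gives K = 102 × 11/8 ≈ 140. With p = 8/11 this *Layout C* gives .959, .802, .844, which also agrees.

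**3. The same layouts with a larger ICC for cohesion**

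The documents give no ICC for cohesion; .10 and .20 are assumed values to show a range.

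| Layout | ICC | DE | n_eff | Power, d = .205 | Power, d = .217 |
|---|---|---|---|---|---|
| A | .10 | 2.121 | 587.1 | .638 | .688 |
| B | .10 | 2.679 | 464.8 | .599 | .648 |
| A | .20 | 3.241 | 384.1 | .465 | .508 |
| B | .20 | 4.357 | 285.7 | .410 | .450 |

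As a worked line, layout A at ICC .10: SE = √[1/(.6818 × 587.1) + 1/(.3182 × 587.1)] = .0886; .205/.0886 − 1.96 = .354; Φ(.354) = .638.

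Layout C is somewhat less sensitive because its platoons are smaller (m = 8.89). At ICC .10, DE = 1.789, n_eff = 695.8 and power is .673 and .722. At ICC .20, DE = 2.579, n_eff = 482.8 and power is .518 and .565.

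These figures use platoon-level clustering only and no gain from baseline adjustment, which is enough to reproduce the plan's own numbers.

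**The case against.** The strongest reply is that this is a label. Section 8a applies one mixed-model approach with baseline adjustment to Hypotheses 2-4, so the estimate, interval and p-value for cohesion are the same under either code, and Aim 4 takes the two hypotheses together. That is correct: the point concerns how a result is attributed, not how it is computed.

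A second reply is that most of these lists are open-ended, and that the H3 power sentence has stray punctuation at its end that may be an incomplete edit or a reading artefact. That weakens the omissions in sections 7b and 8b as evidence. It does not remove the conflict between a hypothesis that names cohesion and a table that gives its only measure the single code 4.

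Three stronger readings are tempting and are not supported:

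- *A reader might infer that error control is damaged, or that outcome families are wrongly drawn.* The plan states no alpha, no multiplicity rule and no families. Family-wise false-positive rates would need an assumed alpha, independent tests and a rule that any one significant outcome suffices. None of these is in the documents, and independence is implausible for self-reports from the same soldiers. The total number of measures is the same under both mappings.
- *A reader might infer that Table 1 is simply the error.* Only the Hypothesis 3 wording names cohesion, which favours that view, but nothing says which text governs. The sponsor has to confirm it.
- *A reader might infer that .80 and .84 are wrong.* They are attainable at the stated ICC. The point is that they do not extend to cohesion.

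**Conclusion.** The inconsistency is real and the other sections do not resolve it. The same cohesion result would be reported under a different hypothesis depending on which text is followed, and under Table 1 Hypothesis 3 loses a component it names. The effect on the analysis itself is nil, so this is a minor point that is cheap to correct.

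The power gap holds under either assignment. Under layouts A and B, power for cohesion is about .60-.64 (d = .205) or .65-.69 (d = .217) at an ICC of .10, and about .41-.47 or .45-.51 at .20. Layout C raises the upper ends to about .67 and .72, and to .52 and .565. These are illustrations: they rest on assumed ICCs, assumed layouts, two-sided .05, and effect sizes the plan took from outcomes other than cohesion. What the documents establish without any of these assumptions is that cohesion is excepted from the small-ICC premise and no power is given for it.

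**What to change.** 1. Have the sponsor confirm which hypothesis cohesion belongs to. The most direct correction is to code Unit Cohesion as Hyp. 3 in Table 1, matching the stated hypothesis. If Hypothesis 4 is intended, amend the wording of both hypotheses instead.
2. Align the descriptions in section 7b and the power text in section 8b with that decision, and use one term for team or unit cohesion throughout.
3. State in section 8b that the .80 and .84 figures at ICC .04 do not cover cohesion, and give power for cohesion over an assumed ICC range, with the number of platoons and the allocation written out.
4. Settle this before results by condition are examined. The current version is dated October 12, 2022, after the anticipated end date of 14 September 2022 in section 4, so that point may already have passed. If it has, report the discrepancy and state which mapping was used.

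The cost of items 1 and 2 is one table entry and a few phrases. Item 3 needs a short calculation rather than a single sentence, because the documents supply no ICC for cohesion. Data collection and the analysis models do not change.
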